3.4.3 Catheter-based radiofrequency ablation

Procedures should be performed on uninterrupted oral anticoagulation and under general anesthesia aiming to complete neuromuscular relaxation (see Appendix 3), with hemodynamic monitoring using a radial arterial line. Single venous femoral access will be mandatory. Peri-procedural anticoagulation will be performed according to local protocols but always aiming to achieve an intraprocedural activated clotting time (ACT) of 300–350 seconds.

Transeptal puncture will be preferably guided by peri-procedural transesophageal echocardiography (TOE), which does not require for an additional venous puncture. Other imaging techniques, such as intracardiac echo, will be allowed to guide the puncture for those centers without TOE availability (it will have to be collected in the data collection sheet). After the puncture, the TOE probe must be removed from the esophagus to avoid tissue overheating during RF applications. The use of a transesophageal temperature probe will be allowed at operator’s discretion. PVI will be performed point-by-point, aiming to

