Acute PVI will be confirmed after *first pass* with the single catheter method of demonstrating entry and exit block with the ablation catheter placed sequentially in each of the PVs or trunks. There is a minimum waiting time of 10 min after isolation of each ipsilateral PV pair; additional RF applications must be performed at reconnection sites until PVI is achieved. A carina line will have to be always performed for the right pulmonary veins, since there is anatomical³⁷ and electrophysiological evidence³⁸⁻⁴⁰ for the presence of interconnections of the ipsilateral veins in up to of $\frac{2}{3}$ of the patients referred for AF ablation.⁴¹ Additional substrate ablation to create left atrial linear lesions or any extra PV-trigger ablation like CFAE is not permitted. Atrial fibrillation that persists after PVI must be terminated with electrical cardioversion. In case other substrates have to be addressed in the same procedure (i.e. right atrial arrhythmias), the additional time, vascular accesses or catheters employed after PVI will not be taken into account for the purpose of the present study.

Of note is that complete PVI will not be considered unless a second evaluating operator confirms the absence of 'visual gaps' along the ablation lines. This second operator may be any experienced professional involved in the procedure (nurse, engineer, technician, etc.) that is able to assess the presence of gaps in a reliable manner. The visual gaps will be defined as any solution of continuity between two RF lesions tagged using the VisiTag settings previously described and a 3-mm tag size. This confirmation will have to be indicated in ALL cases in the data collection sheet. Its absence will be a reason to exclude the case from the study.

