3.5 Outcomes

3.5.1 Primary endpoint

The primary endpoint will be survival free of any atrial arrhythmia at 1-year follow-up. From this endpoint, important definitions must be taken into account:

- AF recurrence will be considered only after the 3-month ‘blinking period’ (see below), whenever the patient refers clear symptoms of recurrence (fast, recurrent palpitations with abrupt onset and termination, lasting for several minutes or hours), if AF is documented in an electrocardiogram (ECG), or whether it is recorded in a Holter registry (> 30 seconds).
- The ‘blinking period’ refers to the first 3-month period after the PVI procedure, where a transient increased risk of post-procedural atrial tachyarrhythmias is expected to occur due to pro-arrhythmogenic inflammatory changes after creating tissue RF lesions.

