3.5.2 Secondary endpoints

3.5.2.1 Acute procedural outcomes

- Procedure time (skin to skin)
- Radiofrequency time
- Number of applications (total/per RF line/per segment)
- Fluoroscopy time
- First-pass isolation rate
- Early PV reconnections

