3.12 Protocol deviation

A protocol deviation is defined as a situation in which there is a non-compliance with the protocol. The following situations are considered protocol deviations and must be appropriately documented:

1. Utilization of another method for guiding the ablation.
2. Ablation of extra PV substrate.

Investigators will be required to adhere to the investigational plan, signed investigator's agreement, applicable national or local, laws and regulations, and any conditions required by the appropriate Ethics Committees or applicable regulatory authorities. The reporting of all the deviations will be performed through the eCRF application. In the event of repeated protocol deviation as determined by the principal investigator, a clinical research associate or clinical representative will attempt to secure compliance by one or more of the following actions: i) contacting the investigator by telephone, or ii) contacting the investigator in writing.

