1. PROCEDURE AND PATIENT DATA

FIRST OPERATOR..... Anesthetist..... EVALUATING OPERATOR.....

DATE OF THE PROCEDURE..... /..... /.....

HR ventilation Yes/No Rate Tidal vol

Age: Sex: Male //Female CHA₂DS₂-VASc = HAS-BLED:... Weight Kg Height: m

CVRF: none // HBP // Dislipemia // DM-2 // Smoker // OSA // Sport (>4 h/week x 10 y)

Underlying HD: none // Hypertensive // Ischemic // HOCM // Valvular // Other

Conduction disturbances: none // LBBB // RBBB // LAHB // LPHB // Other:

Treatment: OAC: Interrupted: Yes // NO // ¿?

TEE LA Size (mm): LVEF: Mitral annulus: cm Other:

PV anatomy: 4 indep. // Left common // Right common // Accessory veins:

LAA Closure: YES // NO Closure device type and size:

2. PROCEDURAL DATA OF PVI:

Number of femoral accesses: 1 / 2 (only 2 permitted in case of ICE use)

Ablation lines adapted to fingerprinted esophagus: YES // NO (why:))

Curve of the ablation catheter (SmartTouch®): Blue // Orange // Black

Procedure time: min FAM + Merge time: min Transeptal time: min

Transeptal puncture technique: TEE // ICE

Fluoro time: sec Fluoro dose: mGy Fluoro dose (index): Gy/cm²

RF power: anterior wall W // posterior wall W

RF time: Right PV s // Left PV s

[figure not shown]
Number of RF points: Left Right

Electrical cardioversion: Yes // No

Acute complications:

Was the procedure evaluated for the absence of gaps by the 2nd operator?: YES // NO

Select at which segment/s the subjacent rhythm was (entirely or predominantly) AF/AT: This is to assess in the future whether segments where rhythm disturbances are observed could influence catheter stability, quality of RF lesions and, ultimately, be a predictor of reconnections.

[figure not shown]
Select at which segment/s **FIRST PASS** isolation was **NOT ACHIEVED**, an explain why:

.....

.....

.....

.....

[figure not shown]
Select at which segment/s **ACUTE RECONNEXION** was observed, an explain why:

.....

.....

.....

.....

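### Same-session right-atrial ablation: time after PVI is to be disregarded while procedure time is skin to skin, and Sections 3.4.3 and 3.12 leave its deviation status open

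*Combined protocol and SAP*

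**What the plan says.** Section 3.4.3 sets a single-access procedure ("Single venous femoral access will be mandatory") and limits what may be added to PVI: "Additional substrate ablation to create left atrial linear lesions or any extra PV-trigger ablation like CFAE is not permitted". It then turns to a different situation, "In case other substrates have to be addressed in the same procedure (i.e. right atrial arrhythmias"), and states that "the additional time, vascular accesses or catheters employed after PVI will not be taken into account for the purpose of the present study". It does not say in terms that such treatment is permitted, but it gives an accounting rule for it.

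Four other places bear on the same patient:

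- Section 3.5.2.1 lists "Procedure time (skin to skin") among the acute outcomes, and fluoroscopy time separately. Section 2.2.2 makes procedure, RF and fluoroscopy time the efficiency objective.
- The Appendix 2 data collection sheet, in its block of PVI procedural data, has one procedure-time field, one fluoroscopy-time field and the item "Number of femoral accesses: 1 / 2 (only 2 permitted in case of ICE use"). RF time is split by right and left PV, and RF points by left and right.
- Section 3.12 lists "Ablation of extra PV substrate" as a protocol deviation that must be documented and reported through the eCRF.
- Section 3.10.3 has the core lab review RF applications from the CARTO exports and makes a violation of the LAWT protocol sufficient reason to exclude a case from analysis.

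**The concern.** Two stated rules pull against each other. A skin-to-skin time contains whatever was done after PVI in the same session; Section 3.4.3 says that this time does not count. Either rule could be followed consistently if the sheet recorded when PVI ended, but the readable sheet does not. Sites can therefore enter different quantities in the same field, and the analyst cannot tell which.

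The status of the case is also open. A site relying on Section 3.4.3 may regard it as compliant and report nothing. A site relying on Section 3.12 may report a deviation. If that deviation is then treated as a violation under Section 3.10.3, the patient leaves the analysis. At stake are the comparability of two secondary efficiency measures across centers and, less directly, who is in the analysis set of a single-arm study whose result is judged against an external protocol (CLOSE) with no concurrent control.

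**Working it through.** The plan gives no figure on this point to reproduce, so the check is mainly a comparison of sections, followed by an illustration of size.

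**1. Which measures are exposed?**

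| Measure | What the plan or sheet records | Can post-PVI work be separated? |
|---|---|---|
| Procedure time | Skin to skin; one field, plus FAM/merge and transeptal times | No: no end-of-PVI time |
| Fluoroscopy time | One field | No |
| Accesses | 1, or 2 only with ICE | Later accesses have no entry |
| RF time | Right PV / left PV | Largely yes |
| RF points | Left / right, in the PVI block | Largely yes |
| First-pass isolation, early PV reconnection | PV-specific | Yes |

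The variable list in Section 3.6.2 has no item for concomitant ablation either. The exposed efficiency measures are therefore procedure time and fluoroscopy time.

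**2. Which status does the case have?** Section 3.4.3 prohibits left atrial lines and extra-PV trigger ablation, then handles right atrial arrhythmias in a separate sentence without prohibiting them. Section 3.12 uses a broader term with no right-atrial exception. Read literally, a right-atrial ablation falls under it. Read as shorthand for what Section 3.4.3 prohibits, it does not. The text does not choose between these readings.

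**3. Size for procedure time.** The documents give neither the share of patients affected (q) nor the added minutes (T). Assume q = 5-20% and T = 15-45 min. If all sites include the added time rather than stopping at end of PVI, the mean rises by q × T:

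- lowest: 0.05 × 15 = 0.75, about 0.8 min
- middle: 0.10 × 30 = 3.0 min
- highest: 0.20 × 45 = 9.0 min

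A mixture of site practices gives a value in between.

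**4. Size if such cases were excluded.** Start from 106 patients less the planned 10% drop-out: 106 × 0.90 = 95.4, taken as 96. Removing 5%, 10% or 20% leaves 96 × 0.95 = 91, 96 × 0.90 = 86 or 96 × 0.80 = 77 (rounded).

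For power, assume a one-sample exact binomial test at one-sided 0.05, a true rate of 91.3% (the CLOSE result in the Introduction, not stated as the planning rate) and a null rate of 91.3 − 10 = 81.3%. Section 3.11.1 gives both a 10% margin and a limit of −0.05; the 10% margin is used here. The critical number r is the smallest with P(X ≥ r | n, 0.813) ≤ 0.05, and power is P(X ≥ r | n, 0.913).

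| n | r | Actual alpha | Power |
|---|---|---|---|
| 96 | 85 | 0.040 | 87% |
| 91 | 81 | 0.034 | 83% |
| 86 | 77 | 0.028 | 79% |
| 77 | 69 | 0.036 | 77% |

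Power falls unevenly because the exact test moves in whole patients. This loss arises only if the exclusion reading is applied.

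**The case against.** The strongest reply is that nothing conflicts. Section 3.4.3 separates prohibited left atrial and trigger ablation from right atrial arrhythmias, and the short item in Section 3.12 can be taken to mirror the prohibited group. The accounting rule can be read as a specific exception to the general skin-to-skin definition. The sheet's time and access fields sit under a PVI heading, and an access field limited to 1 or 2 agrees with ignoring accesses added later. This is a fair reading, but the plan does not state it. Even on it, the sheet does not say when the procedure clock or the fluoroscopy count stops.

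Three stronger inferences might tempt a reader, and the documents do not support them.

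- *That the co-intervention goes untracked.* Deviations are reported in the eCRF, Section 3.8 has a deviation row at every visit, and the core lab reviews RF applications. Capture is inconsistent, not absent. The full eCRF is not in the documents and the sheet's figures are missing, so the lack of a field is shown only for the readable sheet and Section 3.6.2.
- *That complications from added accesses go uncounted.* Section 3.4.3 disregards time, accesses and catheters, not complications. Section 3.5.2.2 collects procedure-related complications, including vascular ones, and Section 3.13 says all complications are documented as secondary endpoints.
- *That the primary result is distorted.* Section 3.5.1 says "The primary endpoint will be survival free of any atrial arrhythmia at 1-year follow-up", which right-atrial treatment could affect, but its working definitions concern AF recurrence. The documents give no frequency or outcome for these patients, so neither the direction nor the size of an effect can be shown.

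**Conclusion.** The point holds in a limited form. The rule disregarding post-PVI time and the skin-to-skin definition are not reconciled, and the readable sheet cannot apply the former uniformly. Procedure time and fluoroscopy time are affected. Separately, Sections 3.4.3, 3.12 and 3.10.3 allow the same case to be compliant, a deviation or excluded. They must be reconciled; this review takes no position on which clinical rule is right.

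The consequence is modest and falls mainly on secondary endpoints: roughly 1 to 9 minutes on mean procedure time under the assumed shares and durations. No threshold or comparator for procedure time is stated, so no decision is shown to turn on it. The power loss from 87% to between 83% and 77% depends on the assumed shares, the assumed test and an exclusion reading that the plan does not clearly adopt. The change is still worth making, because the rules collide as written and an end-of-PVI time is best recorded during the procedure.

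**What to change.** - Reconcile Sections 3.4.3, 3.12 and 3.10.3 so that a same-session ablation of another substrate has one stated deviation status and one stated analysis-set status.
- Add to the data sheet and eCRF: concomitant ablation yes/no and site; clock time and cumulative fluoroscopy time at end of PVI; number of accesses added afterwards.
- Define the efficiency endpoint as skin puncture to end of PVI, treat fluoroscopy time in the same way, and report total skin-to-skin time separately.
- Report how many patients had a concomitant ablation, and add a sensitivity analysis of the primary endpoint without them.

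The cost is a wording change (with IRB approval if it is an amendment under Section 5.3), a few eCRF fields and one extra analysis. It needs no additional patients or procedures. The fields should be in place before enrolment.

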3.5 Outcomes

3.5.1 Primary endpoint

The primary endpoint will be survival free of any atrial arrhythmia at 1-year follow-up. From this endpoint, important definitions must be taken into account:

- AF recurrence will be considered only after the 3-month ‘blinking period’ (see below), whenever the patient refers clear symptoms of recurrence (fast, recurrent palpitations with abrupt onset and termination, lasting for several minutes or hours), if AF is documented in an electrocardiogram (ECG), or whether it is recorded in a Holter registry (> 30 seconds).
- The ‘blinking period’ refers to the first 3-month period after the PVI procedure, where a transient increased risk of post-procedural atrial tachyarrhythmias is expected to occur due to pro-arrhythmogenic inflammatory changes after creating tissue RF lesions.

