3.7 Follow-up

Clinical follow-up (FU) will include outpatient clinic visits at 3, 6 and 12 months after the ablation procedure. If no other contraindications, all antiarrhythmic drugs should be stopped at the 3-month FU visit (end of the 'blinking period'; see 'Outcomes' section before). 12-lead ECG and 24-hour ambulatory Holter monitoring will be performed in every scheduled

appointment. Successful ablation will be defined as the absence of clinical symptoms suggestive of AF recurrence, as well as the absence of documented AF in ECGs and/or Holter.

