3.11 Statistical analysis

3.11.1 Sample size

The sample size calculation has been based on the assumption that the proposed ablation protocol ('LAWT') is an acceptable alternative to the CLOSE protocol¹⁵ (non-inferiority), with the advantage of less radiofrequency applied and likely lower risk for complications. A non-inferiority margin of 10% of clinical success (arrhythmia-free survival one year after the ablation procedure) will be considered to be the largest difference that is acceptable

between both protocols for LAWT to be adopted in clinical practice. Recruiting $n = 106$ participants will be required to confer 90% power to reject the inferiority null hypothesis, that is, that the lower limit of a one-sided 95% confidence interval will be above the non-inferiority limit of -0.05 , indicating no difference between the arms. A drop-out rate of 10% is estimated, and included in the sample size calculation.

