3.11.2 Statistical methods

All applicable statistical tests will be 2-sided and will be performed using a 5% significance level. Continuous variables will be reported as mean \pm standard deviation, or median (range or interquartile range if data are skewed) if not normally distributed; these variables will be compared using Student's t-test if normally distributed or Mann-Whitney U test if not normally distributed. Categorical variables will be expressed as total number (percentage) and will be compared by chi-squared test. For the primary endpoint, survival free from atrial arrhythmia, we will use the Kaplan-Meier survival analysis. A multivariable Cox proportional hazards model will be performed to investigate the effects of baseline characteristics in predicting ablation results, an adjustment will also be done by recruiting center. A receiver operating curve analysis will be performed to determine optimal cutoff LAWT values for predicting AF recurrence after ablation. All efforts will be done to limit missing data on outcome. Nevertheless, missing data will be reported on the final manuscript and, as much as possible, the reasons why data are missing will be documented. If missing, a simple imputation method will be applied and reported.

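### The primary endpoint counts any atrial arrhythmia, but the only event criterion is written for AF and the success definition in 3.7 looks only for AF, so documented atrial tachycardia or flutter is classified in two ways

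*Combined protocol and SAP*

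**What the plan says.** **Wording that covers all atrial arrhythmias.** Section 3.5.1 opens with "The primary endpoint will be survival free of any atrial arrhythmia at 1-year follow-up". Section 3.11.1 sets "A non-inferiority margin of 10% of clinical success (arrhythmia-free survival one year after the ablation procedure". Section 3.11.2 says "For the primary endpoint, survival free from atrial arrhythmia, we will use the Kaplan-Meier survival analysis".

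**Wording that names AF alone.** The first bullet of 3.5.1 says when AF recurrence is counted after the 3-month period. It gives three routes: "whenever the patient refers clear symptoms of recurrence (fast, recurrent palpitations with abrupt onset and termination", or "if AF is documented in an electrocardiogram (ECG), or whether it is recorded in a Holter registry (> 30 seconds". Section 3.7 defines successful ablation as "absence of clinical symptoms suggestive of AF recurrence, as well as the absence of documented AF in ECGs and/or Holter".

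**The comparator.** Section 3.11.1 names the CLOSE protocol as the reference but gives no success rate for it. The only CLOSE rate is in the Introduction: 91.3% at 12 months, reported there as freedom from AF, AT and flutter together. Section 3.1 describes the study as single-arm.

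**The concern.** Two analysts who both follow the protocol could code the same patient in opposite ways on the primary endpoint. One would apply the endpoint sentence and count a documented flutter as a failure. The other would apply the success definition in 3.7 and count that patient as a success. Even an analyst who decides that AT and flutter count has no rule for how they must be documented or how long they must last.

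The design makes this matter more. In a randomised comparison, a narrow event definition would apply to both arms. Here there is no concurrent control, and the external rate counts all three arrhythmias. The Introduction itself attributes recurrence of both AF and AT to gaps left by non-transmural lesions, so AT bears directly on whether lower, thickness-adapted targets are good enough. If the choice is left until results are known, the more favourable reading is open to whoever makes it.

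**Working it through.** The point turns on wording, so no figure in the plan has to be reproduced. The sample size of 106 is taken as stated.

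**Step 1. Is AF used as shorthand for all atrial arrhythmias?** No. The Introduction writes AF and AT as separate items when it discusses recurrence, and lists AF, AT and flutter separately when it gives the CLOSE result. The data collection sheet in Appendix 2 also names AF and AT separately for the underlying rhythm.

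**Step 2. Apply each rule to the same patients.**

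| Patient | Endpoint sentence in 3.5.1; 3.11.1; 3.11.2 | First bullet of 3.5.1 | Success sentence in 3.7 |
|---|---|---|---|
| AF on ECG, or > 30 seconds on Holter, after month 3 | failure | event | not a success |
| AT or flutter after month 3 with the described palpitations | failure | event, through symptoms | not a success |
| AT or flutter documented after month 3, no suggestive symptoms | failure | meets no criterion | success |
| AF on Holter for 30 seconds or less, no symptoms | no threshold given | not an event | not a success |
| AF documented only within the first 3 months | no restriction in the sentence itself | not an event | not a success, read literally |

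The third row is the conflict. The last two rows show that the success sentence in 3.7 also leaves out the > 30 seconds threshold and the 3-month restriction. Section 3.7 does mention the 3-month period and points back to the outcomes section, but only in connection with stopping antiarrhythmic drugs.

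**Step 3. How many patients could this affect?** This is an illustration only, because the protocol gives no split of recurrences by arrhythmia type.

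- Benchmark: 91.3% (Introduction; assumed to be the rate meant in 3.11.1).
- Evaluable patients: 106 × 0.90 = 95.4, taken as 95 (drop-out of 10% from 3.11.1).
- Share of recurrences that are AT or flutter caught by neither the AF criteria nor the symptom route: s = 5-15% (assumed).
- Patients classified differently = 95 × (1 − true success rate) × s.

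| True success rate | Recurrences among 95 | s = 5% | s = 15% |
|---|---|---|---|
| 81.3% (91.3% less the 10% margin) | 95 × 0.187 = 17.8 | 0.9 | 2.7 |
| 86.3% (91.3% less the other stated limit, 0.05) | 95 × 0.137 = 13.0 | 0.7 | 2.0 |
| 91.3% | 95 × 0.087 = 8.3 | 0.4 | 1.2 |

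**Step 4. Direction.** Leaving these patients out of the failures raises the counted success rate against a benchmark that includes such events. Taken alone, that favours a finding of non-inferiority.

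**The case against.** The strongest reply is that the endpoint sentence governs. It is explicit, 3.11.1 and 3.11.2 agree with it, and the first bullet says when AF recurrence is counted without saying that nothing else counts. This is fair as far as 3.5.1 goes: taken alone, that section is incomplete rather than self-contradictory. It does not rescue 3.7, whose success sentence gives the opposite classification. That section does not call itself the primary endpoint, but 3.11.1 equates clinical success with arrhythmia-free survival, so the link is reasonable. Nor does the reply supply the missing criterion for AT and flutter.

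A second reply is that few patients are affected. This stands. The symptom route needs no rhythm documentation, so symptomatic AT or flutter can already be counted. What remains is AT or flutter found on an ECG or 24-hour Holter without suggestive symptoms.

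A reader might also look for support in two other places, and neither provides it. The ROC analysis in 3.11.2 takes AF recurrence as its outcome, but it is a separate predictive analysis and may have its own outcome. The provision in 3.4.3 for treating right atrial arrhythmias concerns the index procedure and says nothing about recurrence afterwards.

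**Conclusion.** The text is wrong as written and should be fixed before the data are analysed. The success rule in 3.7 gives a classification that the stated primary endpoint contradicts, and AT and flutter have no event criterion. This conclusion rests on the wording alone.

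The size is modest: about 0.9-2.7 of 95 patients at the 81.3% limit, and fewer at higher true success rates. Those counts depend on the assumed benchmark, the assumed 95 evaluable patients and the assumed 5-15% share.

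A reader might infer that the trial is biased towards non-inferiority overall. The documents do not support that. Failures declared on symptoms alone push the counted success rate down, and the protocol does not say how CLOSE handled them, so the net direction against the benchmark is unknown. A reader might also infer that the sponsor means to exclude AT and flutter. The endpoint sentence points the other way.

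**What to change.** 1. In 3.5.1, extend the existing documented criteria (on ECG, or > 30 seconds on Holter, after the 3-month period) to atrial tachycardia and atrial flutter.
2. In 3.7 and 3.11.2, replace the separate wordings with a reference to that single definition. This also brings the time restriction and the duration threshold into 3.7.
3. Record the arrhythmia type for each recurrence.

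The cost is a wording change in three sections and one item of data; no extra tests or visits are needed. The downside is that the headline success rate may fall. Under the assumptions above and a true rate of 91.3%, the difference is 0.087 × 0.05 = 0.4 to 0.087 × 0.15 = 1.3 percentage points compared with counting AF and symptoms only. The chance of showing non-inferiority would fall with it, under either of the two limits stated in 3.11.1. In return, the endpoint matches its own headline and counts the same arrhythmias as the only benchmark rate given.
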